1.0 OBJECTIVES

Primary:

- To determine the progression-free survival (PFS) with pazopanib and temsirolimus in patients with advanced poor-risk clear-cell renal cell carcinoma (RCC).

Secondary:

- To determine the objective response rate (CR+PR) in patients with advanced poor-risk clear-cell RCC treated with pazopanib and temsirolimus.
- To determine the overall survival (OS) in patients with advanced poor-risk clear-cell RCC treated with pazopanib and temsirolimus.
- To determine the time to progression (TTP) in patients with advanced poor-risk clear-cell RCC treated with pazopanib and temsirolimus.
- To determine the duration of response in patients with advanced poor-risk clear-cell RCC treated with pazopanib and temsirolimus.
- To determine the safety associated with pazopanib and temsirolimus in patients with advanced poor-risk clear cell RCC.

Tertiary:

- To perform informative correlative studies in this disease state.
- To determine the safety and patient reported outcomes.

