5.4 Evaluation During Treatment (initial treatment or crossover)

*Evaluations while on study will have a standing window of allowance equal to +/- 7 days.

Treatment evaluations will consist of the following study activities (a cycle is 4 weeks):

- Interim medical history and physical examination, including vital signs, height, current weight including recent weight loss every 4 weeks for temsirolimus patients. (May be done by local physician every other cycle for temsirolimus patients only). Interim medical history and physical examination, including vital signs, current weight including recent weight loss every 8 weeks for pazopanib patients.
- All patients will complete a follow-up Quality of Life assessment battery (see Section 7 for additional details)
- Weekly blood pressure monitoring for the first four weeks for patients receiving pazopanib, and then with each history and physical every 8 weeks. Monitoring may be performed at doctor's office or by the patient at home using an electronic blood pressure device. Blood pressure measurements performed outside of the office of the treating physician should be recorded by the patient and submitted to the treating physician during cycle one. An increase in blood pressure to > 160 systolic or > 100 diastolic should be reported to the treating physician immediately.
- Urinalysis (U/A) every 8 weeks. Patients who have urine protein ≥ 300 on U/A should have a random UPC ratio checked for pazopanib patients only.
- Patients on Pazopanib will have serum chemistry and electrolytes including total protein, albumin, alkaline phosphatase, AST, ALT, calcium, LDH, total bilirubin, BUN, creatinine, phosphorus, glucose, sodium, potassium, chloride, and carbon dioxide will be done every 2 weeks for the first 8 weeks and 8 weeks x 2, and every 16 weeks thereafter. Pazopanib patients will have CBC with platelet count and differential every 2 weeks for the first 8 weeks, every 8 weeks x 2, and every 16 weeks thereafter.

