- Patients on temsirolimus will have serum chemistry and electrolytes including total protein, albumin, alkaline phosphatase, AST, ALT, calcium, LDH, total bilirubin, BUN, creatinine, phosphorus, glucose, sodium, potassium, chloride, and carbon dioxide will be done every 2 weeks for the first 8 weeks and every 4 weeks thereafter. Fasting lipid panel every 4 weeks for the first 8 weeks, every 8 weeks x 2, and every 16 weeks thereafter. CBC with platelet count and differential will be done every week for patients on temsirolimus.

- Record concomitant medications with each history and physical.
- Reconcile the medication diary provided during treatment with each history and physical for those on pazopanib.
- Adverse events will be assessed at each visit and monitored throughout the study.
- 12-Lead Electrocardiogram will be repeated at Cycle 2 Day 1, 12 weeks later, and every 16 weeks after that for patients on Pazopanib. (see Section 6.1.1.4 for additional details of QT interval monitoring) Patients receiving temsirolimus will have an ECG done every 16 weeks.
- Optional blood specimens for future correlative studies will be obtained every 8 weeks and at progression.
- Serum amylase and lipase will be obtained only as clinically indicated.
- Serum T4 and TSH will be obtained every 8 weeks for patients receiving pazopanib.
- Repeat radiological studies (CT, MRI as indicated) to evaluate response every 8 weeks. Studies to confirm a complete response or document progressive disease will be performed as needed. Patients who are progression free after 1 year can have their imaging studies obtained every 16 weeks.
- Echocardiogram or MUGA scan (echocardiogram preferred) will be repeated every 24 weeks and as clinically indicated.

Outside Physician Participation During Treatment (Temsirrolimus Patients may have interim infusions with local MD)

1. MDACC Physician communication with the outside physician is required prior to the patient returning to the local physician. This will be documented in the patient record
2. A letter to the local physician outlining the patient's participation in a clinical trial will request local physician agreement to supervise the patient's care (Appendix J); A copy of the protocol abstract and evaluation during treatment will be provided to the local physician with the letter.

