13.0 STATISTICAL CONSIDERATIONS

This is a randomized, two-arm, parallel group, phase II trial enrolling advanced, poor-risk, clear-cell RCC. Patients will be fairly randomized to either temsirolimus (control arm) or pazopanib (experimental arm).

The maximum sample size to be accrued is 90 patients (45 in each treatment arm). The primary measure of efficacy and primary endpoint is progression free survival (PFS). PFS will be monitored on an interim basis and we will use stopping rules for futility to serve as guidelines for early termination. The stopping rules are ad-hoc in nature but are selected in a manner such that the overall type 1 error is controlled at a one-sided 10% with 80% power.

Descriptive and inferential statistics will be used to summarize treatment effects. The mean, standard deviation, median, 25% percentile, 75% percentile, minimum, and maximum will be reported for continuous variables. For discrete variables, descriptive analyses will be based on the distribution of discrete outcomes and will be reported as percentages and patient counts. Time to event endpoints will be descriptively summarized by Kaplan-Meier curves. Point and interval estimates of treatment effect will be based on maximum likelihood methods. For binomially distributed variables, we will report differences in proportions between treatment groups and the 95% confidence interval associated with those differences. We will estimate treatment effects for time to event variables via hazard ratios using Wald scores from Cox proportional hazard regression models. Unless stated otherwise, all statistical tests will be assessed using a two-sided $\alpha = 0.05$ alpha significance level and confidence intervals will be constructed using two-sided 95% and will be based on the normal approximation. Although multiple secondary endpoints will be evaluated we will make no adjustment for multiplicities associated with these multiple tests.

Estimation of Sample Size

The clinical hypothesis we are assessing in this trial is whether patients receiving the experimental therapy have a lower hazard of progression or death relative to patients receiving the control therapy. The statistical hypothesis is stated as:

$$H_0: \log(HR)=0$$

$$H_A: \log(HR)<0$$

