Where HR is the hazard ratio (experimental:control). For sample size calculation purposes we assume that the median PFS in the temsirolimus arm is 60% that of the pazopanib arm (3.8 months versus 6.1 months). The sample size estimate is based on a one-sided log-rank test with type one error equal to 0.10 and power of 0.80.

We will conduct an interim analysis for futility after 42 events have been observed. If the p-value used to assess futility at the interim analysis is greater than 0.4798 we will stop the trial early for futility.

Secondary Objectives

Overall survival: Overall survival is calculated from day of therapy initiation to the date of death. Patients who are lost to follow-up will be censored at date of last contact.

We will use the Kaplan-Meier estimator to estimate the OS for each group of patients (control, experimental), and the log-rank statistic will be used to test for treatment differences. We will also use the Cox proportional hazards regression model to estimate the hazard ratio (experimental:control) for OS with a 95% confidence interval.

We will also assess the response rate and report 95% confidence intervals.

Additional analyses:

Demographics

For each treatment group (control, experimental), summary statistics will be provided for age, weight, baseline disease status and prior treatments.

Toxicities

Toxicities and side effects that will be evaluated include, but are not limited to infections, renal toxicity, hepatic toxicity, and pulmonary toxicity. Methods of assessment will include monitoring blood counts, and performing laboratory tests as indicated by clinical signs and symptoms. Evidence of toxicities or adverse events will be recorded at all clinic visits. All observed toxicities and side effects will be graded (NCI CTC-AE v. 4.0) for all patients and the degree of association of each with pazopanib or temsirolimus assessed. The incidence and severity of toxicities will be compared between the two treatment arms with Fisher's exact test.

Stratification Factors

The Pocock-Simon Minimization Method will be used to randomize patients according to the following stratification factors:

- Prior nephrectomy status (yes or no)
- Prior cytokine/vaccine therapy (yes or no)

The randomization program based on this method will be developed in the Department of Biostatistics and Applied Mathematics, and the program will be available via an intranet web site of MD Anderson Cancer Center.

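### Off-schedule progression may be dated earlier on temsirolimus than on pazopanib because control patients are seen more often, so the one-sided 10% error of the primary PFS test is not guaranteed

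*Combined protocol and SAP*

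**What the plan says.** **Endpoint and test.** Section 1.0 gives the primary objective as "To determine the progression-free survival (PFS) with pazopanib and temsirolimus". Section 13.0 compares the hazard of progression or death with a "one-sided log-rank test with type one error equal to 0.10 and power of 0.80", and says that the "overall type 1 error is controlled at a one-sided 10% with 80% power". It assumes medians of 3.8 and 6.1 months and a maximum of 90 patients (45 per arm). A futility look takes place at 42 events, stopping if p exceeds 0.4798. The final number of events is not stated.

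**Scheduled imaging.** Sections 5.4 and 9.0 give the same plan in both arms: every 8 weeks, with 16-weekly scans permitted after one year free of progression.

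**Clinical contact.** Section 5.4 differs by arm. The history and physical examination includes "current weight including recent weight loss every 4 weeks for temsirolimus patients", against "current weight including recent weight loss every 8 weeks for pazopanib patients". The calendar in Section 9.0 agrees. Under Sections 5.2 and 5.4, temsirolimus patients also come for weekly infusions and weekly blood counts, while pazopanib is taken at home.

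**Unscheduled imaging.** Section 5.4 adds, for either arm: "Studies to confirm a complete response or document progressive disease will be performed as needed". Section 12.0 foresees rapid progression ahead of a scheduled evaluation.

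**Dating.** Section 13.0 does not say how progression found off schedule is dated. It plans no interval-censored analysis and no sensitivity analysis for assessment timing.

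**The concern.** If progression were found only on scheduled scans, the two arms would be dated on the same grid. Unscheduled scans break that. Such a scan needs someone to notice a clinical change, and control patients are seen more often. A progression that becomes apparent soon after a scheduled scan could be dated up to 8 − 4 = 4 weeks earlier on temsirolimus if picked up at the 4-week examination. If it is picked up at a weekly infusion visit, the lead could be up to 8 − 1 = 7 weeks.

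With no drug difference at all, that shortens observed PFS on control and favours pazopanib. No blinding is described, and progression opens crossover to the other agent (Sections 5.1 and 5.6), so there is a practical reason to confirm suspected progression promptly. The issue is the date of the primary event. It is not about adverse-event capture.

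**Working it through.** **1. The plan's own figures.** The hazard ratio is 3.8/6.1 = 0.623. With z-values 1.2816 (one-sided 0.10) and 0.8416 (power 0.80), the squared sum is 2.1232² = 4.508.
- Schoenfeld: 4 × 4.508 / (ln 0.623)² gives 81 events.
- Freedman: 4.508 × (1.623/0.377)² gives 84 events, which is twice the 42-event interim. I therefore take 84 as the final count; this is inferred.
- At 84 events, power is 81.3% without the futility rule. With it, power is 79.4% and overall type I error is 9.4%. The design reproduces, and the futility rule leaves about 0.6 points of slack.

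**2. Why an 8-week grid matters here.** The assumed control median of 3.8 months is 3.8 × 30.44/7 = 16.5 weeks, so one scan interval is about half the median. Under exponential PFS, 2^(−8/16.5) = 71% of events fall after week 8.

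**3. Type I error with equal true PFS.** Assumptions not in the documents: exponential PFS with median 3.8 months in both arms; 84 events, 42 per arm; 15% of events are deaths dated exactly; a given share of control progressions is found at the next clinical contact; the rest, and all pazopanib progressions, are found at the next 8-week scan. The test is a log-rank test at one-sided 10%. With 12,000 trials per cell, the Monte Carlo standard error is about √(0.12 × 0.88/12,000) = 0.3 points.

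| Control progressions found early (pazopanib: none) | 4-weekly contacts | Weekly contacts |
|---|---|---|
| 0% | 10.2% | 10.5% |
| 10% | 11.3% | 12.7% |
| 20% | 12.7% | 14.3% |
| 30% | 14.1% | 16.8% |

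Changing the assumptions:
- **No deaths among the events.** At a 30% share the figures rise to 14.6% and 19.3%.
- **Fuller model** (45 per arm, accrual over 36 months, ±7-day scatter, 15% deaths, analysis at 84 events). At a 25% share: 12.7% with 4-weekly and 13.5% with weekly contacts, or 12.2% and 12.9% once the futility stop is counted.
- **Pazopanib also caught early, at half the control rate.** With 4-weekly contacts and 15% deaths: about 11.5% for 20% v 10%, and 11.5% for 25% v 12.5% in the fuller model (10.7% with the futility stop). With 4-weekly contacts and no deaths: 11.4% for 20% v 10% and 12.4% for 30% v 15%. Weekly contacts without deaths give 12.9% and 13.8%.
- **Equal early detection.** At 30% in both arms without deaths: 10.4% (4-weekly) and 9.9% (weekly). The fuller model gives 10.3% at 25% in both arms.

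**4. Does re-dating remove it?** In the fuller model, every progression was dated to the scheduled assessment. With 25%, 50% and 100% of control progressions found early at 4-weekly visits, the error was 10.2%, 11.0% and 10.8%, or 9.6%, 10.3% and 10.2% with the futility stop. At the design medians and 84 events, simulated power was 79.3% both with 8-week dating and with exact times.

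**The case against.** The strongest reply is that scheduled imaging is identical in both arms and nothing in the documents gives a rate of unscheduled scans. Extra scans are open to either arm. Pazopanib patients have chemistry and blood counts every 2 weeks for the first 8 weeks and weekly blood pressure checks for 4 weeks, and a patient at home with clear deterioration may well call in. A weekly infusion is not a tumour examination. Infusions, and alternate 4-weekly examinations, may be done locally (Section 5.4). Every patient is seen for tumour evaluation every 8 weeks (Section 15.1), and an independent radiology panel re-reads all scans (Section 15.3).

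Much of this stands. A reader might infer that the 10% error is in fact breached. The documents do not support that: with no early detection, or equal early detection, the error stays at about 10%. The zero-detection assumption for pazopanib is a worst case, and the weekly column is the less secure of the two.

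It does not remove the point. The denser pazopanib monitoring is concentrated in the first 8 weeks, before about 71% of events under the assumed median. After week 8, chemistry is 4-weekly on temsirolimus, but on pazopanib it is 8-weekly twice and then 16-weekly. That panel includes LDH and calcium, two of the poor-risk markers in Section 4.1. Local examinations are still examinations, and their findings are reported back. The panel can correct how a scan was read, not when it was taken.

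**Conclusion.** The concern holds as a risk that the plan leaves open. Contact is more frequent on control, off-schedule scans are allowed, and nothing in the analysis guards against a difference in dating. The likely direction favours pazopanib. The one-sided 10% error is not guaranteed and may be exceeded.

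The size rests on assumptions outside the documents: 84 events, exponential PFS with a 3.8-month median, 15% exactly dated deaths, and 10–30% of control progressions found early. On those, type I error is about 11–14% with 4-weekly detection and 12–17% with weekly detection if no pazopanib progression is caught early. It is about 11–12% (4-weekly) if pazopanib is caught at half the control rate, somewhat higher if contacts are weekly, and about 10–11% if detection is equal. The early-detection shares by arm are the deciding unknown, and the trial can record what is needed to judge them.

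**What to change.** Add to Section 13.0, before outcome data by arm are examined:
1. A PFS sensitivity analysis that, in both arms, dates any progression found on an unscheduled scan to the next scheduled assessment (8-weekly, or 16-weekly where that schedule applies after one year), or to death if earlier.
2. A scheduled/unscheduled flag on every scan, with unscheduled scans reported by arm.
3. A stated consequence: a positive primary result that this analysis does not support will be reported as sensitive to assessment timing.

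The flag needs one definition of an on-schedule scan. Section 5.4 allows ±7 days for on-study evaluations and Section 9.0 allows ±3 days; the two must be reconciled.

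The cost is SAP wording, one field per scan and slightly later progression dates in that analysis. There is no material loss of power (about 80% either way). Visit schedules stay as they are.

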2.0 BACKGROUND AND RATIONALE

2.1 Renal Cell Carcinoma (RCC)

Renal cell carcinoma comprises more than 90% of kidney cancer cases and accounts for approximately 2-4 % of all adult malignancies. In 2008, approximately 54,000 people in the United States were diagnosed with kidney cancer (renal cell cancer and transitional cell carcinoma of the renal pelvis) and approximately 13,000 died secondary to metastatic disease. Approximately 25 % of patients with RCC present with metastasis at the time of initial diagnosis and up to 20-30 % of patients develop recurrent disease after nephrectomy. Surgical removal of the primary tumor is the only effective therapy in the non-metastatic setting. No adjuvant therapy has been shown yet to alter the clinical course even in patients at high-risk for developing metastatic disease.

Metastatic RCC (mRCC) is a heterogeneous disease with variable clinical outcome. Two randomized phase III trials have provided support for performing cytoreductive nephrectomy in mRCC, although the most optimal timing of this procedure has not been determined. Some patients with solitary metastasis, who are candidates for complete metastasectomies, can

achieve a long-term survival; however, once metastases develop in multiple organs, systemic therapies, until recently, have had little effect on the clinical course for the majority of patients. Immunotherapy with interleukin-2, interferon-alfa, or a combination of these two cytokines, has been the main therapy in mRCC for two decades, but benefits only a small percentage of patients. In an effort to objectively compare different therapies in the same trial and similar therapies across trials, prognostic models have been developed to assign patients to different risk categories based on pretreatment clinical features. Cytokines (interleukin-2, interferon alfa) have recently been replaced by agents targeting the VEGF or the m-TOR pathways.

2.2 Targeted Therapies in MRCC

Advances in the understanding of the genetic mutation or silencing of the tumor suppressor gene, known as the von Hippel-Lindau (VHL) gene, have shown that this abnormal gene produces a deviant protein which causes the accumulation of hypoxia inducible factors (HIF), which in turn induce the production of products which are critical to the proliferation of clear-cell RCC. Three of these products are vascular endothelial growth factor (VEGF), platelet derived growth factor (PDGF), and transforming growth factor-alpha (TGF- α). All four of these cellular products, i.e., HIF, VEGF, PDGF and TGF- α , have constituted rational targets of novel therapies.

Pazopanib is a multi-tyrosine kinase inhibitor that selectively inhibits protein tyrosine kinase receptors including VEGFR1-3, PDGFR α/β , c-Kit, and Flt-3. Pazopanib demonstrated substantial anti-tumor activity in a phase II trial in mRCC with randomized discontinuation design (Hutson et al, 2009). A randomized phase III trial comparing pazopanib to placebo, either as first-line therapy in treatment-naïve patients, or after failure of one cytokine in 435 patients with advanced clear-cell RCC showed significant prolongation of median PFS in favor of pazopanib (9.2 months vs. 4.2 months for all patients, $p < 0.0000001$; 11.1 months vs. 2.8 months for treatment-naïve patients, $p < 0.0000001$; 7.4 months vs. 4.2 months for cytokine-pretreated patients).

Temsirolimus is an inhibitor of mTOR (mammalian target of rapamycin). Temsirolimus binds to an intracellular protein (FKBP-12), and the protein-drug complex inhibits the activity of mTOR that controls cell division. Inhibition of mTOR activity resulted in a G1 growth arrest in treated tumor cells. When mTOR was inhibited, its ability to phosphorylate p70S6k and S6 ribosomal protein, which are downstream of mTOR in the PI3 kinase/AKT pathway was blocked. In in vitro studies using renal cell carcinoma cell lines, temsirolimus inhibited the activity of mTOR and resulted in reduced levels of the hypoxia-inducible factors HIF-1 and HIF-2 alpha, and the vascular endothelial growth factor. The clinical benefit of temsirolimus for poor-risk, advanced RCC patients was demonstrated in a Phase III study comparing temsirolimus, with interferon alpha (IFN-alpha), or combined temsirolimus plus IFN-alpha as first-line treatment of advanced RCC. It showed that treatment with temsirolimus alone significantly increased median overall survival in poor-risk, advanced RCC patients (10.9 vs 7.3 vs

8.4 months). This was the first Phase III trial to demonstrate an overall improvement in survival using an agent as "targeted therapy" for patients with advanced RCC.

The targeted agents discussed above, although not curative, represent a significant progress in the management of mRCC.

2.3 Rationale

In the past few years, considerable progress has been made in the management of patients with metastatic renal cell carcinoma (RCC). There are now six (five in the first-line setting) FDA-approved treatments for metastatic RCC, however most patients experience disease progression within a year or less. The vast majority of metastatic RCC patients who were enrolled on phase 3 trials with anti-VEGF therapies, sorafenib, sunitinib, pazopanib and bevacizumab plus interferon alfa had good- or intermediate-risk disease. Temsirolimus is the standard of care for the treatment of patients with advanced poor-risk RCC, based on results from a phase 3 trial comparing single-agent temsirolimus versus single-agent interferon alfa versus the combination of temsirolimus and interferon alfa. The response rate of temsirolimus in this study was 8.4 %, and the median PFS and median OS were 3.8 months and 10.9 months, respectively. There is no data on the efficacy of multityrosine kinase inhibitors (TKI) in this disease state. Therefore, it is important to investigate agents with the oral convenience and tolerability of TKIs, such as pazopanib, in advanced poor-risk RCC.

